Exploratory Study on Effect of Whitening Agent with Emulsion Gel in Xerostomic Population

Principal Investigator: [name], DMD, MS

Co-Investigators: [name], DMD, PhD

Study Coordinators:

[name], AS, CDA, CCRP

[name], BS, CCRP

[name], RDH [name]

Study Location: Tufts University School of Dental Medicine

[name]

Sponsor: Procter & Gamble

Protocol Version Date: 4/14/2023

Exploratory Study on Effect of Whitening Agent with Emulsion Gel in Xerostomic Population [name], DMD, MS

I) Introduction

A) Aim/Hypothesis/Objective

Objectives:

- Primary aim: To see a reduction in the self-reported subjective perception of dryness in the oral cavity.
- Secondary aims: To measure self-reported sensitivity of the teeth, self-reported
 perception of teeth whiteness, and objective measurement of improvement of saliva
 production.

II) Background and Rationale

Xerostomia, is a subjective sensation of dryness of the mouth, which may have a significant effect in a persons quality of life. The sensation of dryness of the mouth may be caused by autoimmune diseases which attack the saliva producing glands irreversibly e.g., salivary glands, or the sensation of dryness could be caused by therapeutic radiation, which can destroy the salivary glands at the genetic level and impede their functions. Additionally, there are more than 700 medications including antihypertensives, anti-anxiety agents, psychiatric remedies, and antihistamines that can effect neural transmission. Neural transmission is when the neuro transmission is hindered reversibly leading to the salivary hypofunction that results in dry mouth. It is estimated that 12-47% of the elderly and 10-19.3% in their early 30's suffer from dry mouth (6)(7). In a study, it was found that the prevalence of xerostomia was 10.0% (with no apparent gender difference) among 32-year-olds and was significantly higher among those taking antidepressants (odds ratio =4.7) (5). At risk groups may present much higher (60+%) rates of xerostomia. A systemic literature review suggests a prevalence of 27 –32% of the medicated population suffer from xerostomia as a side effect (7).

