The product being used is a commercially available product, known as "Crest Whitening Emulsions", will be used as the investigative product. There will be no active control group. This is not the first time P&G whitening gel will be used in humans. We do believe this is the first study investigating dry mouth sensation from using a whitening gel.

- III) Research Plan
 - A) Experimental Design

This will be a single center, two visit study investigating the effectiveness of dryness in the oral cavity, whiteness of teeth, and teeth sensitivity after one week's use of whitening agent.

B) Sample Size and Statistical Analysis

Sample size

This is a single site study. All study-related procedures will take place at TUSDM. Based on our preliminary data from a previous study, we anticipate 25 subjects will be needed to achieve the necessary statistical power required to observe expected differences in relief of dryness in the oral cavity. Because we anticipate the potential of many screen failures due to the VAS scale and saliva production requirements outlined in the exclusion/inclusion criteria section, we will screen/enroll a total of 100 subjects to conservatively account for potential dropouts or screening failures.

Statistical analysis

The subjects will be asked to complete one questionnaire each visit. Completing the first part before the application of the study product, and completing the second part after the application of the study product, as directed on the questionnaire. The self-reported scores from the visual analogue scales (VAS) will be considered on the first and final visit. The salivary flow before and after the application of the product, Pre & Post-Product Use Dry Mouth & Sensitivity Questionnaire before and after the product application will be compared using a student -t test method. The same method will be used to make comparisons of these gathered data points between the first and final visits.

Randomization

This will be an open label study; thus no randomization plan is necessary.

Blinding

There will be no blinding for this study.

C) Products

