Non-English speakers will be excluded from the study because the study team does not have validated questionnaires developed in multiple languages. The study team also does not have the resources to translate the take home diary or manufacturer's

instructions. In addition, the visual demonstration of the application of the study product will not be able to be effectively translated using the Interpreter Machine available at TUSDM. There are no physical translators available at TUSDM to assist in translating the visual demonstration. There are no direct benefits to this population by participating in this study.

E) Assessment

1) Risk

The standard risk associated with teeth whitening products include causing gum irritation, gum or teeth bleaching, teeth sensitivity, and irritation of the oral mucosa (cheeks, lips, tongue). In addition, there is a risk of irritation or whitening from contact with skin from using this study product. Subjects may also feel discomfort when they abstain eating or drinking before the study visit.

There is the risk of loss of confidentiality to the subject by participating in this study. This risk will be kept to a minimum by following procedures listed under confidentiality section.

2) Benefits

There is no direct medical benefit to the subject for participation in this study. However, the results of the study will help better understand whether the application of hydrophobic emulsion containing agents have a beneficial effect in alleviating subjective sensation of mouth dryness along with teeth whitening in a Xerostomic population. The results of this study will help in understanding the contributing factors that alleviate dry mouth and increase esthetics through whitening of teeth.

3) Alternatives

Patients may choose not to participate in the study and to receive the standard of care treatment for dry mouth at TUSDM at normal clinic fees.

F) Study Procedures

Visit 1 (1-1.5 hours) Screening/ Baseline (Day 0)

- 1. Subject will be called 1-2 days before their appointment to confirm that in order to participate, they must:
 - a. Not consume alcohol for 24 hours prior to their visit.
 - b. Not brush their teeth for 1.5 hours prior to their visit.
 - c. Not have had anything to eat or drink (including chewing gum or eating candy) for 1.5 hours prior to their visit). Water is acceptable to drink up to 1 hour prior to the study visit.
 - d. Not smoke 1.5 hours prior to their visit.

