- The subjects will be asked to read the informed consent form (ICF). Subjects will
 be given ample time to have any questions answered. If a subject decides to
 participate, he or she will be asked to sign the ICF. A copy of the ICF will be given
 to the subject.
- 3. Subject will be asked to complete demographic information and a medical history.
- 4. An oral exam, including evaluation of oral cavity, soft and hard tissues, will be completed following standard of care procedures in US dentistry using a mouth mirror and dental explorer.
- 5. Subject medications with potential side effects being dry mouth will be verified using the Physician's Reference Desk.
- 6. Saliva Collection 1 (pre-product application): Saliva will be collected by asking subjects to do nothing but drool into a pre-weighed vial for 5 minutes (referred to as the Drooling Method). The post collection weight will be subtracted from the pre-weight to determine the flow rate. The saliva samples will be discarded after they are weighed.
- A paper questionnaire will be given to subject to complete before application of study product and after application of study product. Questionnaire includes Visual Analogue Scale (VAS) questionnaire on dry mouth, quantity of saliva, and perceived sensitivity of teeth.

- 8. Inclusion/exclusion criteria will be evaluated and eligibility for the study will be determined.
- 9. Demonstration and application of study product:
 - a. A visual and oral demonstration of application of the whitening gel will be performed by a study team member. The script for the demonstration will be the one provided in the information packet in each study product box so the subject can bring the instructions home. The study team member will mimic the necessary steps to properly apply the gel, without using the product. The study team member will then have the subject complete the steps while applying the gel to their own teeth. Subjects will then be asked to sit for 5 minutes to let the gel set on their teeth.
- 10. Saliva Collection 2 (post-product application): Saliva will be collected using the same Drooling Method as Saliva Collection 1. The saliva samples will be discarded after they are weighed.

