- 11. Photographs of subject teeth will be taken by a standard dental camera. The photos will only contain subject teeth and oral cavity with no subject identifiers visible. In addition to the ICF, the subjects will be asked to sign a photo release form. If the subject does not wish to sign this form, their photographs will not be taken. Those who do not consent to having their photos taken will be tracked in the enrollment log. Photographs will be taken pre-application of the study product at visit 1.
- 12. Distribution of study product and diary: One box of study whitening gel product, (0.88Oz) toothpaste, and a toothbrush will be dispensed by study team members. This is to ensure all participants are using the exact same dental products during the trial period. The subjects will be asked to not use any other oral tools or products during the trial period aside from the ones distributed by the study team at Visit 1. A diary will also be dispensed for the record keeping of the application of the products. A study team member will again verbally tell the participant the instructions that are provided with the study product and that per the

instructions, they can apply the product up to 4 times per day until their next study visit. The same script from step 9.a. will be used.

13. Gift card will be distributed upon successful completion of visit.

Visit 2 (1-1.5 hours) Final Visit - 7 ∓ 2 days after visit 1

- 1. Subject will be called 1-2 days before their appointment to confirm that in order to participate, they must:
 - a. Not consume alcohol for 24 hours prior to their visit.
 - b. Not brush their teeth for 1.5 hours prior to their visit.
 - c. Not have had anything to eat or drink (including chewing gum or eating candy) for 1.5 hours prior to their visit). Water is acceptable to drink up to 1 hour prior to the study visit.
 - d. Not smoke 1.5 hours prior to their visit.
- 2. Medical history will be reviewed, and any changes will be noted. Any changes to medications will also be reviewed and noted.
- 3. Eligibility and subject withdrawal criteria will be reviewed to ensure the subject still qualifies for the study.
- 4. Subject medications with potential side effects being dry mouth will be verified using the Physician's Reference Desk. Subjects will be asked to confirm that they have taken their medications as prescribed since Visit 1.

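### Self-reported tooth whiteness is one of three secondary aims, but no measure described in the plan captures it

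*Combined protocol and SAP*

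**What the plan says.** All references are to the combined protocol and SAP.

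- **Aims (I.A).** There are three secondary aims: self-reported sensitivity, self-reported whiteness and measured saliva production. The last two are worded as "perception of teeth whiteness, and objective measurement of improvement of saliva" production.
- **Design (III.A).** The design statement names whiteness again, as something the study investigates: "whiteness of teeth, and teeth sensitivity after one week's use of whitening agent".
- **Questionnaire (III.B and III.F).** III.B states: "The subjects will be asked to complete one questionnaire each visit". III.F, Visit 1, step 7 gives its content: "Questionnaire includes Visual Analogue Scale (VAS) questionnaire on dry mouth, quantity of saliva, and perceived sensitivity of teeth". Visit 2, step 7 gives the same three topics. Section III.D and the schedule table title the form by dry mouth and sensitivity only.
- **Analysis (III.B).** The general sentence is "The self-reported scores from the visual analogue scales (VAS) will be considered on the first and final visit". The specific one covers salivary flow and the named form: "Pre & Post-Product Use Dry Mouth & Sensitivity Questionnaire before and after the product application will be compared using a student -t test method". A further sentence extends the same method to comparisons between the first and final visits.
- **Photographs (III.F, Visit 1, step 11).** These need a separate release: "If the subject does not wish to sign this form, their photographs will not be taken".
- **Benefits (III.E.2).** The results are expected to show whether such agents have a "beneficial effect in alleviating subjective sensation of mouth dryness along with teeth whitening in a Xerostomic population".

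**The concern.** A stated aim needs a variable, and here the link is missing. Sensitivity, the other self-reported secondary aim, appears in both the form's title and its content list; whiteness appears in neither. If the form matches its description, the study will finish with nothing to report on this aim.

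Timing adds to the problem. The study is open-label with a single arm, so within-subject change is the only comparison available. Subjects apply the gel for the first time during Visit 1 (III.F, step 9). A rating from before any treatment must be taken before that step, so an omission found later cannot be fully repaired for subjects already treated.

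**Working it through.** The plan gives no figure to reproduce on this point. The check sets each source of data against the aim.

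| Source | What the plan says it captures | Self-reported whiteness? |
|---|---|---|
| Questionnaire, Visit 1 (III.F, step 7) | Dry mouth, saliva quantity, sensitivity | Not described |
| Questionnaire, Visit 2 (III.F, step 7) | The same three topics | Not described |
| Diary (III.F, Visit 1, step 12) | Product applications | No |
| Photographs (III.F, Visit 1, step 11; Visit 2, step 10) | Images of the teeth; optional; no rater, scale or analysis given | No |
| Oral exam (III.F, both visits) | Soft and hard tissues | No |
| Saliva collections (III.F, both visits) | Weight of drooled saliva | No |
| Schedule table (17 rows) | No row is a whiteness rating | No |

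**Aims against measures.** Sensitivity has a VAS at both visits. Saliva production has a weighed collection at both visits. Whiteness has no described measure. So 2 of 3 secondary aims have a described measure and 3 − 2 = 1 does not. The primary dryness aim has its VAS.

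**Where the word occurs.** *Whiteness* appears twice, once in the aims (I.A) and once in the design statement (III.A). It does not appear in the procedures, the schedule or the analysis text.

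**Number of ratings if an item is added.** Question 1 of the pre-product questionnaire is an inclusion criterion (III.D.1), and the questionnaire (III.F, Visit 1, step 7) comes before the eligibility decision (step 8). Everyone screened therefore completes the Visit 1 pre-product part. III.B plans to screen or enroll 100 and says 25 are needed.

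- Visit 1: up to 100 ratings.
- Visit 2: about 25 ratings, assuming about 25 subjects continue.
- Total: up to 100 + 25 = 125, giving about 25 pairs for the comparison.

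**The case against.** The strongest objection is that the form has not been seen. The word *includes* need not be exhaustive, so a whiteness item may already be on the paper. A reader might infer from the two content lists that no whiteness data will be collected. The documents do not support that; they support only the narrower statement that no described measure captures the aim. This part of the objection stands, and it makes checking the form the first step. It does not remove the point, because an existing item would still be missing from both descriptions.

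A reader might also infer that the analysis plan would have nothing to say about whiteness even if an item existed. That goes too far: the general VAS sentence and the first-to-final comparison in III.B would cover it. The gap lies in the measurement.

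It can be said that the photographs inform whiteness. They could bear on the design statement and the benefits text, neither of which says self-reported, although no rating of them is described. They cannot answer an aim about the subject's own perception.

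Finally, a rating just after the first application might serve as an imperfect baseline, and a rating at Visit 2 alone would give some weaker information. The documents give no figure for whitening after a single application, so neither can be called useless. Neither is an untreated baseline.

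**Conclusion.** The point holds in limited form. One of three secondary aims, self-reported whiteness, has no described measure. If the form matches its description, the aim has no data, and an untreated baseline is lost for each subject at the first application. The first statement is certain from the text; the consequence depends on a form that is not in the documents.

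The study is exploratory and the aim is secondary, so this should be corrected but does not threaten the trial. A reader might infer that the dryness result is weakened; it is not, and neither are the sensitivity and saliva aims, which have measures at both visits.

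**What to change.** 1. Check the questionnaire form for a perceived-whiteness item.
2. If there is none, add one VAS item to the pre-product part at both visits. Whether the item is new or already there, list it in III.F (Visit 1, step 7 and Visit 2, step 7).
3. Analyse it as the within-subject change from the Visit 1 pre-product rating to the Visit 2 pre-product rating, under the first-to-final comparison already in III.B.
4. If the sponsor does not want the item, remove self-reported whiteness from the secondary aims in I.A and check that the whiteness wording in III.A is still supported. Removing the self-report aim does not by itself require that wording to go.

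**Cost.** One line on a paper form and a protocol amendment, which III.L makes subject to prior IRB and sponsor agreement. The ratings to enter are those counted above. No visit or staff is added. The change is worth most before further subjects make their first application.

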- An oral exam, including evaluation of oral cavity, soft and hard tissues, will be completed following standard of care procedures in US dentistry using a mouth mirror and dental explorer.
- 6. Saliva Collection 1 (pre-product application): Saliva will be collected using the drooling method for 5 minutes into a pre-weighed vial. The post collection weight will be subtracted from the pre-weight to determine the flow rate. The saliva samples will be discarded after they are weighed.
- 7. The paper questionnaire will be given to subject to complete before application of study product and after application of study product. The questionnaire

- includes the Visual Analogue Scale (VAS) questionnaire on dry mouth, quantity of saliva, and perceived sensitivity of teeth.
- 8. Application of study product: A study team member will ask the subjects to apply the gel to their teeth. Subjects will then be asked to sit for 5 minutes to allow the gel to set on their teeth.
- 9. Saliva Collection 2 (post-product application): Saliva will be collected using the same drooling method as Saliva Collection 1. The saliva samples will be discarded after they are weighed.
- 10. Photographs of subject teeth will be taken by a standard dental camera. The photos will only contain subject teeth and oral cavity with no subject identifiers visible. Photographs will be taken post-application of the study product at visit 2.
- 11. The study diary and any leftover whitening gel product will be collected.
- 12. Gift card will be distributed upon successful completion of visit.

	Screening/ Baseline Visit Day 0	Visit 2 Day 7 (±2 days)
Informed Consent Form	X	Day 7 (±2 days)
Demographics	X	
Collect and/or Review Medical History	X	Х
Review eligibility and withdrawal criteria		Х
Confirmation of Xerogenic Medications	Х	
Pre-Product Use Dry Mouth & Sensitivity	Х	Х
Questionnaire		
Post-Product Use Dry Mouth & Sensitivity	x	Х
Questionnaire		
Unstimulated Salivary Test	x	Х
Oral Exam	x	Х
Evaluate eligibility criteria	x	
Oral Photographs	X (Pre-Application)	X (Post-Application)
Demonstration of Product Use	х	
Product Usage	X	X

Post Product Use Unstimulated Salivary Test	х	х
Product Distribution or Collection	X	X
Adverse Event Reporting (if applicable)	Х	Х
Stipend	Х	Х

G) Subject Safety

1) Adverse Event Reporting

Adverse Events

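### No saliva collection starts from an emptied mouth, and only Collection 2 follows a fixed 5-minute gel sit, so the within-visit flow comparison can show a rise without any change in production.

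*Combined protocol and SAP*

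**What the plan says.** The secondary aims (I.A) include an "objective measurement of improvement of saliva" production. It is the only aim described as an objective measurement.

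The method is set out in III.F, Visit 1, step 6: "Saliva will be collected by asking subjects to do nothing but drool into a pre-weighed vial for 5 minutes". The rate comes from the weight difference: "The post collection weight will be subtracted from the pre-weight to determine the flow rate". Nothing is deducted, and no step empties the mouth before timing starts.

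At Visit 1, step 9a, the subject applies the gel and then: "Subjects will then be asked to sit for 5 minutes to let the gel set on their teeth". The next numbered step is Collection 2: "Saliva will be collected using the same Drooling Method as Saliva Collection 1". Visit 2, steps 8 and 9, follow the same order: "Subjects will then be asked to sit for 5 minutes to allow the gel to set on their teeth", then the second drool. Neither visit's steps say whether the subject may swallow during the set, or should spit, rinse or remove gel before the second collection.

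III.B compares "The salivary flow before and after the application of the product" with a Student t test. There is no control group and no blinding.

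**The concern.** A timed flow rate is valid only if the vial receives what was produced during the timed period. Saliva already in the mouth at time zero is credited to those 5 minutes. If the amount were the same before and after product, it would largely cancel in the difference. The plan gives no assurance of that. Collection 2 always follows 5 minutes of sitting with a hydrogen peroxide gel on the teeth, when some reluctance to swallow is plausible. Collection 1 follows a medication check (Visit 1) or an oral exam (Visit 2), with no prescribed sit.

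A net excess in the second vial would look like the effect that the Background section hopes for, namely that the gel promotes saliva flow. Without a control group that sits for 5 minutes with no gel, the data cannot separate retained saliva from new production. Subjects must also have low flow to enter, so small retained volumes are large in relative terms.

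**Working it through.** **Inputs from the documents.** Entry ceiling for unstimulated flow: 0.18 mL/min (III.D). Collection time: 5 min. Gel set: 5 min (III.F). Sample size: 25 (III.B). The documents give no mean or SD of flow, no alpha, no sidedness, no statement of paired or unpaired testing, and no information on how much saliva subjects retain. The figure of 25 is justified for relief of dryness, not for flow. It cannot be reproduced from what is stated, and nothing below depends on reproducing it.

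**Assumptions.** Production F is unchanged by the gel. At the start of Collection 2 the mouth holds a fraction f of the saliva produced during the set, that is f × 5F. At the start of Collection 1 it holds g × 5F. Take 1 g as 1 mL.

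**Step 1: apparent rates.**
- Collection 1: (5F + g × 5F)/5 = F(1 + g)
- Collection 2: (5F + f × 5F)/5 = F(1 + f)
- Apparent relative change: (f − g)/(1 + g)

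If g = 0, the false rise equals f. If both are zero or equal, there is no bias. If f = 0.25 and g = 0.10, the false rise is 0.15/1.10 = 13.6%. If g exceeds f, the change is falsely negative.

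**Step 2: scale at the entry ceiling, with g = 0.** Collection 1 gives 0.18 × 5 = 0.90 mL.

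| f | Collection 2 volume (mL) | Apparent rate (mL/min) | False rise |
|---|---|---|---|
| 0 | 0.90 | 0.18 | 0% |
| 0.10 | 0.99 | 0.198 | 10% |
| 0.25 | 1.125 | 0.225 | 25% |
| 0.50 | 1.35 | 0.27 | 50% |

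In absolute terms, 0.2 mL retained is 0.2/0.9 = 22% of the collection.

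**Step 3: chance of p<0.05 with no true change.** Assume a paired t test, two-sided 5%, n = 25 (critical t with 24 df = 2.064), on relative change with an assumed SD. The noncentrality is f/SD × √25. For example, 0.25/0.50 × 5 = 2.5 gives 67%.

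| Assumed SD of relative change | f = 10% | f = 25% | f = 50% |
|---|---|---|---|
| 30% | 36% | 98% | over 99% |
| 50% | 16% | 67% | over 99% |
| 80% | 9% | 32% | 85% |

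Here f is the average over the whole sample. On the absolute scale, with an assumed mean flow of 0.10 mL/min and SD of the difference of 0.10 mL/min, the same three values of f give about 8%, 22% and 67%.

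**Step 4: only some subjects retain saliva.** If each subject has a one-in-five chance of retaining 25%, the sample average is 0.2 × 25% = 5%. Simulation at SD 50% gives about 8%, close to the nominal 5%. If one in five retains 50% (average 10%), it gives about 14%.

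**Step 5: after the fix.** Emptying the mouth before both collections sets f = g = 0. The apparent change is then 0%, and the test keeps its nominal 5% as far as this mechanism is concerned.

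**The case against.** The strongest reply is that retention is supposed, not documented. The protocol says only that subjects sit; it does not forbid swallowing. If they swallow as usual, f is near zero and nothing is biased. That stands, and it is why the point is about an uncontrolled step and not a demonstrated error.

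A reader might infer that the error sits only in the second vial and can only push upwards. The documents do not support that. Collection 1 has no emptying step either, and at Visit 2 it comes directly after an oral exam, when saliva could also pool. Only the difference between the two residuals biases the comparison. The fixed sit makes an upward net error the more plausible direction, but no more than that.

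A reader might also take the 67% or over-99% figures as the expected false-positive rate, or expect a doubling of flow. Those figures need the whole sample to average 25% or 50% retention on an assumed scale and SD, and a doubling needs every subject to retain everything for 5 minutes. Nothing in the text points to such amounts.

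Three further limits stand:
- The product packet that supplies the demonstration script is not in the documents and may mention spitting or swallowing.
- That Collection 2 starts at once is inferred from step order. No interval is given, and the post-product questionnaire could come in between.
- Flow is a secondary aim of an exploratory study, and the Visit 1 versus Visit 2 comparison of pre-product flow is not touched by the gel set.

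None of these supplies the missing step. The packet governs gel application, and nothing shows that it standardises saliva collection.

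**Conclusion.** The concern holds in a limited form. Residual saliva is uncontrolled at all four collections, and the conditions before Collection 1 and Collection 2 differ in a way that can produce a within-visit rise without any change in production. With no control group, a significant rise could not be read with confidence as increased production.

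The size is unknown. The false rise is (f − g)/(1 + g), which is zero under normal swallowing and 10% to 50% if the sample averages f = 0.10 to 0.50 with g = 0. The chance of a spurious p<0.05 runs from near nominal (about 8% when one subject in five retains 25%) to 67% (sample-average f of 25%). Both figures assume n = 25, a paired two-sided 5% test and an SD of relative change of 50%. The plan states none of these except the 25.

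The change is worth making because it is cheap and protects the one objective aim. It also standardises Collection 1, which decides eligibility against 0.18 mL/min.

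**What to change.** Add to the Drooling Method, for both collections at both visits: *Immediately before the 5-minute clock starts, the subject empties the mouth into a waste cup (not weighed); timing starts then.* At Collection 2 this comes after the set has ended, so the 5-minute set is not shortened.

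The cost is one sentence, a cup and a few seconds per collection. There are two downsides to accept openly:
- Saliva produced during the set is no longer counted, although any taste stimulation would already be acting then. The protocol should state that the post-product rate refers to the 5 minutes after the set.
- The step does not remove the weight of gel shed into the vial, and emptying the mouth may dislodge some gel. About half a teaspoon is applied, roughly 2.5 mL. If 10% reached the vial (an assumption, at density about 1), it would add 0.25/5 = 0.05 mL/min. That needs its own handling.
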